8 EFFICACY ANALYSES

In general, efficacy analyses will be performed on the ITT set (or the ITT-2 set).

Interceding therapies are defined as new treatment for AML including salvage treatments and hematopoietic stem cell transplantation (HSCT).

8.1 PRIMARY EFFICACY ANALYSIS

The primary efficacy endpoint is overall survival (OS) measured as the time from randomization until death from any cause. The primary set of analysis will be the ITT set.

OS time for patients alive at their last assessment of survival status will be right censored

- At the documented date of the last assessment during follow-up (which should finally correspond to the date reported in the end of long-term follow-up) in the CRF, in the case that the long-term follow-up is filled in,
- At the last assessment of survival status available in the case that the long-term follow-up is not filled in.

OS will not be censored at the time of subsequent interceding therapies, if the patient received any. Final analysis will take place after the required number of events (390 deaths) has occurred or after the decision to stop the trial because of futility or superiority at time of the interim analysis.

Missing start or end dates for the calculation of OS will be imputed as described in section [6.1.1](#).

The primary OS analysis will be based on the log-rank test stratified by ECOG PS and cytogenetic risk (both ECOG PS and cytogenetic risk values used for the randomization) comparing the two survival functions of the active treatment group and placebo at the overall one-sided alpha = 0.025 level of significance (a group sequential design according to Gamma family spending function, adopting $\gamma=-3.6$ (similar to O'Brien Fleming) for superiority and $\gamma=-5.5$ (more conservative than O'Brien Fleming) for futility (non-binding)) is used).

Additionally, the duration of the follow-up will be calculated using a reverse KM analysis, considering an event in patients who are alive and censoring patients at their date of death.

8.1.1 Interim Analysis

The efficacy analyses done for the interim analysis by the unblinded statistician at the CRO will be provided to the IDMC, which will provide a recommendation to Sponsor whether the study should proceed or stop due to efficacy or futility (non-binding). The efficacy criterion, which will be the basis for the IDMC recommendation together with the overall risk-benefit assessment is that the p-value of the stratified log-rank test is below the computed significance level of the interim analysis (p-value <0.00605). For the futility the significance level of 0.29906 is computed as the bound. In terms of HR, the following values are calculated: 0.73254 for the efficacy and 0.93671 for the futility evaluation, respectively. Significance levels and their counterpart in terms of HR will be re-computed at time of analysis based on the real fraction of information available. Conditional power of getting a significant result at the final analysis taking into account the results of the interim analysis will also be computed. In case of stopping of the study at the interim stage, correction to the estimation (median estimate and related CI) will be applied to reduce potential bias. Adequate SAS code will be used to produce the stratified log-rank test (PROC LIFETEST), save the test results and pass these results to the PROC SEQTEST together with the needed data from the PROC SEQDESIGN. Elaboration of data from PROC LIFETEST could be needed considering that the alternative hypothesis is one-sided.

Boundaries at time of the Interim Analysis (IA) will be recomputed having as fraction of information the number of events at IA in the ITT set / overall number of planned events (390). For calculations, the power of the test will be changed as needed to maintain the initial total number of events (390).

The proportionality of hazards will be exploratively evaluated plotting the log negative log survival distribution function for each of the treatment groups in each stratum against the log of survival days.

Selected secondary endpoints could be analyzed to provide additional information to the IDMC, if requested .

8.1.2 Final Analysis

The efficacy criterion, is that the p-value of the stratified log-rank test is below the computed significance level of the final analysis (p-value <0.02314). In terms of HR, the following value is calculated: 0.81723. Significance levels and their counterpart in terms of HR will be re-computed at time of analysis based on the real fraction of information available.

At the final stage the following analyses will be done (if the study is stopped at the interim analysis, all procedures/tests described below, as well as those related to the secondary endpoints, will be performed but considered only as exploratory; PROC SEQTEST will not be performed):

Stratified log-rank test. The proportionality of hazards will be exploratively evaluated plotting the log negative log survival distribution function for each of the treatment groups in each stratum against the log of survival days.

Appropriate methods of estimation will be applied to take into account for the sequential design. PROC SEQTEST will be adopted with the input of relevant data from PROC LIFETEST and PROC SEQTEST run at IA.

The following analysis will also be performed:

- Stratified log-rank test maintaining patients in the cytogenetic risk category assessed by the central laboratory and the ECOG PS grade as documented at Day 1 as sensitivity analysis.
- Unstratified log-rank test and Cox (PH) model including strata (cytogenetic risk factor and ECOG grade as randomized) as covariates in the model will be used as a sensitivity analysis to support evidence of efficacy. Ties will be handled using the “Efron method” in SAS. Interaction terms of the strata with the treatment groups will not be included in the model.

The proportional hazards assumption will be exploratively evaluated by including the time dependent covariate Time x Treatment and by plotting for each covariate in the model the standardized score process of the actual data against simulated patterns based on the PH assumption (option ASSESS of SAS PROC PHREG)

- Kaplan-Meier estimates of OS in each treatment group will be reported, both overall and within strata of patients. Estimates of median survival will be provided with two-sided 95% confidence intervals, along with the first and third quartile (Q1 and Q3).
- Estimation of the hazard ratio of the two treatments by means of the Cox PH model including stratification factors and treatment.
- The number of surviving patients, the number of deaths and the number of patients with censored values will be displayed as well.
- Censoring patterns will be examined between treatment groups. Therefore the censored and not censored observations in the two treatment groups will be analyzed over time in a scatterplot.
- The effect of subsequent therapy on OS will be analyzed, including an analysis that compares OS in the treatment groups with censoring at the start date of the new interceding therapy, including those started during study treatment phase (concomitant therapy) and after stopping of study treatment as recorded in the new AML therapy eCRF page. Balance of such cases in the two treatment groups will be assessed to evaluate the appropriateness of this analysis method.
- Other sensitivity analyses will be performed to assess the robustness of OS results, if relevant. These will be decided prior to unblinding (e.g. at BDRM) based on real data.
- The primary OS analysis (stratified log-rank test) will be repeated for the PP set.
- Impact on OS of other baseline/demographic factors (including those considered for the subgroup analysis (section 5.3), plus possible others), will not be evaluated by means of Cox PH model(s) as initially planned due to the evident lack of the PH assumption for the treatment group factor.

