5.4 MULTIPLE COMPARISONS AND MULTIPLICITY

Secondary endpoints will be tested according to a fixed sequence method. If the primary endpoint is statistically significant, then the first secondary endpoint (according to the predefined list) will be tested, and so on for the other three secondary endpoints. When the sequence stops for a non-significant test the following tests will be downgraded to exploratory.

The secondary efficacy outcome measures for this study are ordered as follows:

- Morphologic CR rate
- Transfusion independence
- CR_{MRD}-rate
- CR_c rate

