5.5 SIGNIFICANCE LEVEL

The overall significance level for the primary efficacy endpoint is 0.025 (one sided). As an interim analysis according to the O'Brien Fleming function for superiority and the Gamma family function (with $\gamma=-5.4695$ for non-binding futility) will be done after 260 events (2/3 of the total number of events), the respective significance levels are 0.00605 for the interim and 0.02314 for the final analysis. These significance levels will be re-computed at time of analysis based on the real fraction of information available.

Calculations of significance levels and related thresholds were performed by means of SAS PROC SEQDESIGN.

The following table shows probabilities to stop at interim analysis for futility or superiority with the null and alternative hypotheses for the primary endpoint:

Table 1 Probability to stop at Interim Analysis HA as Median OS	10 months	14 months
Gamma spending function $\gamma=-5.4695$ for futility	0.70094	0.01442
O'Brien Fleming for superiority	0.00605	0.58059

The following table shows probabilities of significant results for the first secondary endpoint, according to the chosen hierarchical procedure and assuming no need to consider the correction for multiplicity as 100% of information would be collected (which was the assumption at time of SAP V1). The reference alternative hypothesis is that the difference between treatments in the CR rate is 0.13 (having 0.20 as the rate for the placebo group). Probabilities are corrected by unconditional probability of significant results for the primary endpoint as conditional probability assumes the correlation between endpoints to be known. The obtained results are conservative and represent the lower probability bound assuming no correlation.

Table 2		
Secondary endpoint(s)		
Assumption: 100% information for secondary endpoint at interim analysis is available		
probability of significant results	0.13 rate difference	
	Independent from primary endpoint (i.e. as it was the only endpoint in the study)	Hierarchical procedure *
at Interim Analysis	0.91	0.55
Overall	0.91	0.82

* rounded power for the primary endpoint is 0.90 overall and 0.60 at interim analysis, respectively (median OS = 14 months vs. 10 months)

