However, it is now assumed that not all the patients could be recruited at time of interim look or some of them could not be followed-up for enough time and considering that correlation between the primary endpoint and the secondary endpoints cannot be assumed to be null even if difficult to quantify (no correlation would have justified not correcting for multiplicity), a procedure that manages the multiplicity due to having planned for an interim analysis is needed. The Bonferroni correction (with 0.002 and 0.023 as the partition of the overall alpha level) will be adopted, regardless of the quantity of patients and the time of follow-up. Interpretation of p-values will be based on the hierarchy defined in section 5.4. The family-wise error rate of 0.025 will be adhered to [2, 3].

According to current recruitment rate, 85% of patients on average will have been recruited before the interim analysis time.

The O'Brien Fleming bound for the primary endpoint and Bonferroni criterium for the secondary endpoint(s) will then be adopted, leading to the probability of significant results being as reported in the following table.

Table 3		
Secondary endpoint(s) - probability of significant results at Interim/Final Analysis		
Assumptions: 85% of patients randomized and Bonferroni (0.002, 0.023)		
	0.13 rate difference	
	Independent from primary endpoint (i.e. as it was the only endpoint in the study)	Overall Hierarchical procedure **
Probability of significant results at Interim Analysis	0.56	0.34
Probability of significant results Overall	0.82*	0.74

power for the primary endpoint is rounded to 0.90 overall and 0.60 at interim analysis (median OS = 14 months vs. 10 months)

*assuming 0.6 as the probability to obtain significance at FA given failure at IA (as not all the 85% of patients will have been followed-up for more than 6 months)

** performing test on secondary endpoint also at FA in the case the primary is significant at IA but secondary is not

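### If an interim OS win stops the trial, SAP 8.1.2 makes the later CR test exploratory, yet Table 3's overall 0.74 counts that test; without it the figure is about 0.58 on Table 3's own inputs

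*SAP*

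**What the plan says.** - **Gate to the secondaries.** SAP 5.4: "If the primary endpoint is statistically significant, then the first secondary endpoint (according to the predefined list) will be tested". CR comes first, then transfusion independence, CR without MRD and cytogenetic CR.
- **Alpha for the secondaries.** SAP 5.5: "The Bonferroni correction (with 0.002 and 0.023 as the partition of the overall alpha level) will be adopted". This is one-sided 0.002 at the interim and 0.023 at the final analysis. SAP 8.2 refers back to 5.5 for the procedure.
- **Success probabilities for CR.** SAP 5.5, Table 3, reports 0.56 (interim) and 0.82 (overall) for CR taken alone, and 0.34 and 0.74 under the hierarchy. Its footnotes give the ingredients: "power for the primary endpoint is rounded to 0.90 overall and 0.60 at interim analysis"; "assuming 0.6 as the probability to obtain significance at FA given failure at IA"; and, for the hierarchical column, "performing test on secondary endpoint also at FA in the case the primary is significant at IA but secondary is not".
- **Effect of a stop.** SAP 8.1.2 opens its list with "At the final stage the following analyses will be done". A parenthesis adds that, after an interim stop, the listed tests, "as well as those related to the secondary endpoints, will be performed but considered only as exploratory". SAP 8.1 says the final analysis follows either 390 deaths or an interim decision to stop for futility or superiority.
- **Whether crossing means stopping.** Table 1 in SAP 5.5 is introduced as giving "probabilities to stop at interim analysis for futility or superiority". SAP 8.1.1, however, has the IDMC weigh overall risk and benefit and make a recommendation, and protocol 3.2 says only that the study may end early.
- **Secondaries at the interim.** The last line of SAP 8.1.1 says selected secondary endpoints could be analysed for the IDMC if it asks.

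**The concern.** After a superiority stop, two parts of the SAP give the same CR test different standing. Table 3 treats a CR test at the final analysis, following an interim OS win and a CR miss at 0.002, as part of the confirmatory procedure. SAP 8.1.2 makes final-stage secondary tests exploratory once the study has stopped, whatever the reason for stopping.

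This affects the most likely route to success. Under the design alternative about 64% of OS wins come at the interim (0.5806/0.9087). On that route it is unclear whether a CR result that misses 0.002 has a second confirmatory chance at 0.023. Under the fixed sequence the same doubt passes to the three endpoints behind CR. Two things are at stake: an overstated success probability for the first secondary endpoint, and a confirmatory status that could be settled after results are known.

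**Working it through.** **Inputs.** From Table 3 and its footnotes: OS power 0.60 at the interim and 0.90 overall, so 0.30 won only at the final analysis; CR power 0.56 at the interim; conditional CR probability 0.6 at the final analysis after an interim miss. From SAP 5.5: CR 0.20 versus 0.33 and 85% of patients randomised at the interim. From protocol 9.11: 500 patients, so 250 per arm, or 212.5 per arm at the interim. The SAP multiplies OS and CR probabilities, that is, it assumes no correlation.

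**Step 1: reproduce Table 3.**
- CR at the interim, pooled-variance z-test, 212.5 per arm, one-sided 0.002: 0.5635 (SAP 0.56).
- Interim, hierarchical: 0.60×0.56 = 0.336 (SAP 0.34).
- Overall, CR alone: 0.56 + 0.44×0.6 = 0.824 (SAP 0.82).
- Overall, hierarchical: 0.90×0.824 = 0.742, or 0.90×0.82 = 0.738 (SAP 0.74).

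The last line applies the full interim-plus-final CR probability to every OS win, including the 0.60 won at the interim.

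**Step 2: remove the retest after an interim OS win, assuming that win stops the trial.**
- Retest term: 0.60×0.44×0.6 = 0.158.
- What remains: 0.60×0.56 + 0.30×0.82 = 0.336 + 0.246 = 0.582 (0.583 with 0.824).
- Loss: about 0.16, roughly one fifth of 0.74.

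**Step 3: vary the inputs.** With 260 of 390 events, hazard ratio 10/14, one-sided bounds 0.00605 and 0.02314, and the futility bound 0.29906 obeyed, OS crosses at the interim with probability 0.5806 and only at the final analysis with 0.3281, total 0.9087. These match the SAP's 0.58059 (Table 1) and 90.87% (section 3.3). CR power at 250 per arm and one-sided 0.023 computes to 0.905; the SAP does not give this figure.

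| Inputs | With retest | Without retest |
|---|---|---|
| Table 3 as printed | 0.74 | 0.60×0.56 + 0.30×0.82 = 0.58 |
| Unrounded OS power | 0.9087×0.824 = 0.75 | 0.5806×0.56 + 0.3281×0.824 = 0.60 |
| CR 0.905 where OS wins only at the final | 0.60×0.824 + 0.30×0.905 = 0.77 | 0.60×0.56 + 0.30×0.905 = 0.61 |
| Both changes | 0.5806×0.824 + 0.3281×0.905 = 0.78 | 0.5806×0.56 + 0.3281×0.905 = 0.62 |

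**Step 4: a stop is not certain.** If a share s of interim crossings leads to a stop, the overall figure on Table 3's inputs is about 0.74 − 0.16s: 0.66 at s = 0.5, 0.58 at s = 1, and 0.74 at s = 0.

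**The case against.** **Crossing need not stop the trial, and the retest is disclosed.** Both are true. The footnotes state the retest and label the 0.6 as assumed, and if follow-up runs to 390 deaths the retest takes place and 0.74 holds. What Table 3 lacks is the condition that the trial continues, and Table 1 labels the same event as stopping.

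**The clause has a purpose after a futility stop.** A reader might infer that it matters only after a superiority stop, since the secondaries need an OS win. The documents do not support that. A final analysis also follows a futility stop, futility is non-binding, and 8.1.2 sets an OS criterion of 0.02314; the clause prevents that OS test from being read as confirmatory and opening the sequence. The conflict with Table 3, however, arises only after a superiority stop.

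**The replacement figure depends on assumptions too.** SAP 5.5 describes its no-correlation results as a lower bound and then says the correlation cannot be taken as null. In a joint-normal model with the SAP's bounds and CR rates, 212.5 then 250 per arm, and no fixed 0.6 conditional, the overall probability without the retest is 0.62, 0.65, 0.68 and 0.71 at assumed OS–CR correlations of 0, 0.2, 0.4 and 0.6. The gap to the printed 0.74 then shrinks to 0.03–0.12, although the retest itself still contributes 0.14–0.20 in that model. So 0.58 is the figure on Table 3's own terms, not a general estimate.

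**The consequence is limited.** The trial is sized on OS, no power target is set for CR, and SAP section 11 says the secondary-testing proposal is still under FDA review. This keeps the point modest; it does not reconcile the two passages.

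**Conclusion.** The point holds as an inconsistency conditional on a superiority stop. In that case 8.1.2 removes the confirmatory retest that Table 3 counts, and the overall CR probability falls from 0.74 to about 0.58 on Table 3's inputs (0.58–0.62 with unrounded OS power, computed final-analysis CR power, or both). This assumes that crossing the OS bound leads to a stop, that OS and CR are uncorrelated, and that the 0.002 interim CR test remains confirmatory.

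Two stronger readings go beyond the documents. A reader might infer that 8.1.2 also downgrades the 0.002 interim test, leaving only 0.30×0.82 = 0.25. The clause belongs to the list of final-stage analyses, and 5.5 and 8.2 provide for an interim test, so that reading is not established; but the on-request wording in 8.1.1 leaves the interim test's status less clear than it should be. A reader might also infer a threat to type I error. There is none: 0.002 + 0.023 = 0.025, the OS test and its boundaries do not change, and calling post-stop tests exploratory is conservative.

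**What to change.** Reconcile SAP 8.1.2, 5.5, 8.2 and the last line of 8.1.1. State explicitly whether the ordered secondary tests are confirmatory or exploratory (a) at one-sided 0.002 at the interim once OS has crossed, and (b) at 0.023 after a superiority stop. Then make Table 3 agree, in one of two ways:

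- restate the overall hierarchical figure as about 0.58, naming the stop and no-correlation assumptions; or
- keep 0.74 with a footnote that it holds only if the trial continues to the final analysis after an interim OS win.

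If the exploratory clause is instead limited to futility stops, the retest stays confirmatory and 0.74 can remain as the SAP computes it.

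Whichever status is chosen needs a dated justification made without reference to results, because SAP section 11 says version 5 reflects changes decided after the interim results were unblinded. This applies equally to confirming the 0.002 test and to keeping the 0.023 test. The cost is a few sentences across these sections, one figure or footnote, and the justification. Data, alpha and boundaries do not change.

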3.3 SAMPLE SIZE CONSIDERATIONS

This is an event-driven study. Sample size was computed for a group-sequential design with stopping rules for both futility and superiority (study-wise one-sided alpha level=0.025, power 0.90) with one interim analysis at 67% (2/3) of information and a final analysis. The alpha error spending function is from the O'Brien Fleming function for superiority and the Gamma family (with $\gamma=-5.4695$, more conservative than O'Brien Fleming) for futility (non-binding). Proportionality of hazards is assumed. Assuming that median OS is 10.0 months in the Group B (placebo + AZA) the aim is to detect, by means of the log-rank test or equivalent, an increase to 14.0 months in Group A (pracinostat + AZA), i.e. a HR of 0.714286. A total of 390 events (deaths) allows to meet a power requirement of at least 90% (actually 90.87%; it was 90% with the original function used in v1 protocol; further calculations kept fixed the number of events needed) at a study-wise one-sided significance level of 0.025.

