11 CHANGES TO THE PLANNED ANALYSES IN THE PROTOCOL

Version 2 of SAP was based on protocol version 3. The version 3 of the SAP reflects changes due to study protocol version 5. Version 4 of the SAP reflects minor changes needed to be implemented after the first dry-run of the data (before the Interim Analysis) and tuning of the rules for the new AML therapy. Version 5 of the SAP reflects changes decided before and during the BDRM for Final Analysis (after unblinding of the results of the Interim Analysis). Due to FDA request the following changes were applied in the SAP, which are not reflected in the study protocol:

- 1) Change of the function for performing the superiority test according to a group sequential design for the primary endpoint as requested by FDA
- 2) Change of the parameter of the function for performing the futility test according to a group sequential design for the primary endpoint, in order to maintain the same probabilities to stop for true and wrong futility
- 3) Change of the method to test for secondary endpoints to overcome some possible issues reported by FDA. The new proposal by Helsinn is under further review of FDA
- 4) Details on the interceding therapies have been included
- 5) Imputation rules for interceding therapies have been included

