13 SUMMARY OF PLANNED EFFICACY ANALYSES

At the BDRM it might be decided not to perform any analyses for the PP set (depending on the number of patients to be excluded from the ITT set) and to add analyses for sensitivity and / or additional subgroups.

Type of endpoint	Endpoint	Analysis set	Stratification	Test	Other feature	Relevance
primary	OS	ITT	ECOG, RISK (randomization)	Log-rank	none	Primary analysis for this endpoint
primary	OS	ITT	ECOG (Day 1 Cycle 1), RISK (centralized)	Log-rank	none	sensitivity
primary	OS	ITT	none	Log-rank	none	sensitivity
primary	OS	ITT	ECOG, RISK (randomization)	Cox PH	none	sensitivity
primary	OS	ITT	ECOG, RISK (randomization)	Log-rank	Censor at time of new therapy	sensitivity
primary	OS	PP	ECOG, RISK (randomization)	Log-rank	none	Secondary set
primary	OS	ITT	ECOG, RISK (randomization) + other factors	Cox PH	none	Exploratory Factors and related levels to be decided at BDRM
First secondary	CR	ITT	ECOG, RISK (randomization)	CMH	none	Primary analysis for this endpoint
First secondary	CR	EE-1	ECOG, RISK (randomization)	CMH	none	Secondary set
First secondary	CR	ITT	none	LRT	none	sensitivity
First secondary	CR	EE-1	none	LRT	none	Sensitivity on secondary set

First secondary	CR	ITT	ECOG, RISK (randomization) + other factors	Logistic regression	none	Exploratory Factors and related levels to be decided at BDRM
Second secondary	Transfusion independence	ITT	ECOG, RISK (randomization)	CMH	none	Primary analysis for this endpoint
Third secondary	CR _{M RD} -	ITT	ECOG, RISK (randomization)	CMH	none	Primary analysis for this endpoint
Third secondary	CR _{M RD} -	EE-1	ECOG, RISK (randomization)	CMH	none	Secondary set
Fourth secondary	CRc	ITT-2	ECOG, RISK (randomization)	CMH	none	Primary analysis for this endpoint
Fourth secondary	CRc	EE-2	ECOG, RISK (randomization)	CMH	none	Sensitivity on secondary set
Explorative	cCR	ITT	ECOG, RISK (randomization)	CMH	none	Primary analysis for this endpoint
Explorative	cCR	EE-1	ECOG, RISK (randomization)	CMH	none	Secondary set
Explorative	BR	ITT	none	none	none	Primary analysis for this endpoint
Explorative	BR	EE-1	none	none	none	Secondary analysis for this endpoint
Explorative	RFS	ITT	ECOG, RISK (randomization)	Log-rank	none	Primary analysis for this endpoint
Explorative	RFS	ITT	ECOG, RISK (randomization)	Log-rank	Censor at time of new therapy	sensitivity
Explorative	PFS	ITT	ECOG, RISK (randomization)	Log-rank	none	Primary analysis for this endpoint

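### The SAP says proportional hazards evidently fail for treatment, yet leaves the Cox hazard ratio unqualified as the only explicitly specified between-group effect size for overall survival

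*SAP*

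**What the plan says.** The design rests on proportional hazards. SAP section 3.3 states "Proportionality of hazards is assumed" and sizes the trial on medians of 10 and 14 months, "i.e. a HR of 0.714286". The interim and final criteria are also expressed as HRs: 0.73254 (efficacy) and 0.93671 (futility) at the interim in section 8.1.1, and 0.81723 at the final analysis in section 8.1.2.

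Section 8.1.2 then treats the Cox model in three ways:

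- Models of other baseline factors on OS will not be run, "due to the evident lack of the PH assumption for the treatment group factor".
- The treatment effect is still to be estimated: "Estimation of the hazard ratio of the two treatments by means of the Cox PH model including stratification factors and treatment".
- The unstratified log-rank test and a Cox model with the strata as covariates "will be used as a sensitivity analysis to support evidence of efficacy".

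Proportionality is checked only in an exploratory way (log-negative-log plots, a time-by-treatment term, score-process plots). No rule says what to report if the checks fail. Section 13 still carries an OS row for a Cox model with other factors, with the note "Factors and related levels to be decided at BDRM".

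Two further points give context. Section 11 says version 5 contains "changes decided before and during the BDRM for Final Analysis (after unblinding of the results of the Interim Analysis"). Section 8.1.2 says that if the study stops at the interim, the listed analyses "will be performed but considered only as exploratory; PROC SEQTEST will not be performed".

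**The concern.** If proportionality for treatment fails badly enough to cancel exploratory covariate models, it also fails in the model that supplies the treatment HR. The SAP acts on the finding in one place and ignores it in the other.

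Without proportional hazards, the Cox HR is a weighted average of a changing ratio. The weights depend on when deaths occur and when patients are censored, so two analyses of the same true survival curves, one at 260 deaths and one at 390, estimate different numbers. A reader given one HR and its confidence interval would not know that. No between-group OS measure free of the assumption is specified: no milestone difference, no restricted mean difference, no HR by period. Protocol section 9.5 does plan survival probabilities at selected time points, but SAP sections 5.6 and 8.1.2 do not carry them over.

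**Working it through.** **1. The plan's own figures, which assume proportional hazards.** Inputs from SAP sections 3.3, 5.5, 8.1.1 and 8.1.2: 390 deaths, interim at 260, HR 10/14, one-sided 0.025, O'Brien-Fleming spending for superiority and Gamma (-5.4695) for futility. With information = deaths/4, the HR bound is exp(-z/√(deaths/4)).

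| Bound | Nominal p | z | Calculation | Result | SAP |
|---|---|---|---|---|---|
| Interim efficacy | 0.00605 | 2.509 | exp(-2.509/√65) | 0.7325 | 0.73254 |
| Interim futility | 0.29906 | 0.527 | exp(-0.527/√65) | 0.9367 | 0.93671 |
| Final efficacy | 0.02314 | 1.993 | exp(-1.993/√97.5) | 0.8172 | 0.81723 |

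Power from the group-sequential calculation is 90.87%, as stated. There is no arithmetic error.

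**2. Does the Cox HR move with follow-up?** Inputs from protocol section 9.11: control median 10 months, 100 patients in year 1 and 400 over the next 18 months, 3% yearly drop-out, 1:1 allocation. The limiting Cox HR is exp(b), where b solves

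∫ G(t) { S₁h₁ - [eᵇS₁/(S₀ + eᵇS₁)] (S₁h₁ + S₀h₀) } dt = 0.

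Here G(t) is the number per arm who could have been followed to t by the analysis date, net of drop-out, and S and h are the survival and hazard in each arm. The analysis date is set where expected deaths reach 260 or 390. Under proportional hazards 390 deaths are expected at month 47.4, consistent with the planned 30 + 18 months.

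The non-proportional patterns below are assumptions; the documents give none.

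| Assumed HR over time | Cox HR at 260 deaths | Cox HR at 390 deaths | Shift |
|---|---|---|---|
| 0.714 throughout | 0.714 | 0.714 | 0 |
| 1.0 to month 3, then 0.60 | 0.722 | 0.679 | -0.04 |
| 1.0 to month 6, then 0.60 | 0.822 | 0.749 | -0.07 |
| 1.3 to month 4, then 0.6 | 0.890 | 0.787 | -0.10 |
| 1.25 to month 6, then 0.65 | 0.997 | 0.888 | -0.11 |
| 0.60 to month 6, then 1.0 | 0.775 | 0.835 | +0.06 |
| 0.65 to month 6, then 1.25 | 0.899 | 0.983 | +0.08 |

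The 1.3-then-0.6 row is a separate illustration; simulation gave 0.78 to 0.79 at 390 deaths. The other non-proportional rows come from a set of 12 patterns whose shifts ran from -0.11 to +0.08.

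**3. Which measures do not move?** Take the 1.3-then-0.6 pattern, with λ = ln 2/10 = 0.0693 per month.

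- Survival, pracinostat vs placebo: at 4 months exp(-1.3 × 4λ) = 0.70 vs exp(-4λ) = 0.76; at 24 months exp(-5.2λ - 12λ) = 0.30 vs exp(-24λ) = 0.19. These targets are the same at either analysis.
- Mean survival time restricted to 24 months: 12.83 vs 11.69, a difference of 1.13 before rounding, again the same at either analysis.
- With the horizon set instead at the smaller of the two arms' longest follow-up times, the horizon moves from about 29.5 months at 260 deaths to 42.8 at 390. The difference moves with it, from 1.76 to 3.10 months.

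A restricted mean therefore solves the problem only if its horizon is fixed in months.

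**The case against.** The strongest reply is that the Cox HR was prespecified. Protocol section 9.7.1 names both the Cox sensitivity model and the HR estimates, and replacing them after the interim results were known would be worse than keeping them. That stands: the HR should stay, and anything new should be added and labelled as late.

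The SAP also reports more than an HR. Section 8.1.2 gives Kaplan-Meier medians and quartiles for each arm and stratum, diagnostics for proportionality, and estimation adjusted for the sequential design. Section 8.1.1 plans a corrected estimate if the trial stops early, and section 9.2.5 summarises deaths within 30, 60 and 90 days. So a reader might infer that the Cox HR is the only numerical result, or that an early harm would go unseen. The documents support neither. What is missing is an explicitly specified between-group OS measure that does not need proportional hazards.

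The supportive role is also limited: no efficacy decision rests on the Cox model, and after an interim stop these analyses are exploratory. This softens the point, but the HR would still be reported without qualification.

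Finally, the illustrated shifts come from chosen patterns, and even their direction is open. That is correct, and is why a range is given.

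**Conclusion.** The inconsistency is in the text and should be corrected. The SAP declares that proportionality fails for treatment, cancels one set of models for that reason, leaves the treatment HR untouched, and still lists the cancelled model in Section 13.

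The size is conditional. Under the protocol's accrual, drop-out and control median, the Cox HR shifts between 260 and 390 deaths by about -0.11 to +0.08 over the 12 assumed patterns. For scale, the interim efficacy and futility bounds are 0.93671 - 0.73254 = 0.20 apart. The actual pattern, and so the actual size and sign, cannot be read from the documents.

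Three stronger readings are not supported:

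- That the primary test is invalid. The stratified log-rank test keeps its type I error when the survival curves are equal. Power and the HR versions of the bounds do rest on proportionality.
- That the trial showed early harm with late benefit, or the reverse. No pattern is described.
- That the remark came from the unblinded interim data. The timing of version 5 makes this possible, but the SAP does not say what the evidence was.

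**What to change.** Keep the stratified log-rank test as the primary analysis. In SAP section 8.1.2:

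1. Report between-group differences in Kaplan-Meier survival with 95% CIs at fixed milestones, for example 6, 12, 18 and 24 months. This restores, with named times, the survival probabilities planned in protocol section 9.5.
2. Report the difference in restricted mean survival time with 95% CI at a horizon fixed in months, for example 24 months if both arms have follow-up to that point. Do not tie the horizon to the longest observed follow-up.
3. Keep the prespecified Cox HR, label it as an average over the observed follow-up, and do not describe it as supporting efficacy without that caveat.
4. Make Section 13 agree with section 8.1.2 on the model with other factors.

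Label items 1 and 2 as specified after the interim unblinding. As an option, the covariate models could be run with treatment as a stratum, which needs no proportionality for treatment and so removes the stated reason for dropping them.

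The cost is wording, standard programming and a few extra supportive estimates. The primary test, the alpha and the event count do not change.
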